## **9.7. Clinical Laboratory Evaluations**

Safety laboratory assessments will include hematology, serum chemistry, coagulation, and urinalysis.

- Coagulation (only at Screening): prothrombin time, international normalized ratio, and partial thromboplastin time
- Hematology: CBC including hemoglobin, hematocrit, white blood cell count with 5 part differential (including ANC), red blood cell, and platelet count
- Serum chemistry: bicarbonate, calcium, phosphorus, magnesium, albumin, glucose, serum creatinine, uric acid, total protein, urea, AST, ALT, lactic dehydrogenase, alkaline phosphatase, total and direct bilirubin, sodium, potassium, and chloride
- Routine urinalysis: dipstick and microscopy (if indicated), including protein, specific gravity, glucose, and blood
- Serum or urine  $\beta$ -HCG pregnancy test

At Screening, either GFR or the estimated serum creatinine clearance (mL/min) as an estimate of GFR will be calculated. The estimated serum creatinine clearance rate (CrCl; mL/min) will be calculated using the modified Cockcroft-Gault equation ([Appendix 17.1](#)). The estimated GFR will also be calculated before each cisplatin or carboplatin administration. This will be performed only until completion of chemotherapy.

All laboratory values must be assessed by the Investigator as to clinical significance. All abnormal laboratory values considered clinically significant by the investigator or NCI

CTCAE Grade  $\geq 3$  should be recorded on the AE page of the eCRF. If the abnormal laboratory value constitutes an SAE, a SAVER form should be submitted and other relevant procedures must be followed (see Section 9.4.2). Abnormal laboratory values (NCI CTCAE Grade 3 or 4) occurring during the clinical study will be followed until repeat test results return to normal (or baseline), stabilize, or are no longer clinically significant.

## **9.8. Vital Signs**

Vital sign measurements include blood pressure, heart rate, temperature, height, and weight.

## **9.9. Electrocardiograms**

A 12-lead ECG will be performed within 14 days prior to Screening, at the End-of-Study Treatment visit, and during the study at the discretion of the Investigator.

## **9.10. Physical Findings**

Physical examinations will evaluate the following body systems/organs: respiratory, cardiovascular, gastrointestinal, musculoskeletal, genitourinary/reproductive (optional), psychiatric (optional), hematological, neurological, immunological, head, eyes, ears, nose and throat, and other. Abnormal physical examination findings that are new or changed will be reported as AEs; otherwise, physical examination observations will not be recorded.

## **9.11. Other Safety Assessments**

### **9.11.1. Echocardiograms or MUGA (LVEF Assessment)**

To monitor for possible effects of treatment on cardiac function, LVEF will be assessed at Screening, Cycle 3, and then every third subsequent cycle, the End of Treatment Visit, and as otherwise clinically indicated using either echocardiography or MUGA scanning (if MUGA is considered local standard of care). The same test must be used for a subject throughout the study. Clinically significant changes from baseline in LVEF will be reported as AEs.

### **9.11.2. Human Antihuman Antibodies**

The presence of anti patritumab neutralizing antibody in serum will be assessed. Blood samples will be taken on Day 1 of Cycle 1 (preinfusion), Cycle 2 (preinfusion), Cycle 3 (preinfusion), and at End-of-Study Treatment visit. A PK sample will be collected at the same time of HAHA collection for interpretation of HAHA results, which will be provided to the study sites. For subjects with positive anti patritumab neutralizing antibody on the serum sample drawn at the end of study treatment visit, additional serum samples should be obtained for antibodies, until the antibody level returns to baseline (or becomes negative) or up to 1 year from the last dose of study drug or if the subject starts another therapy for cancer, whichever occurs first.

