### **6.2.9. End of Study Treatment Visit (21 days after last dose)**

At the end of study treatment, the following procedures will be performed.

- Physical examination
- Vital signs
- Weight
- ECOG Performance Status (Section 10.1)
- Perform an echocardiogram or MUGA scan
- Perform a 12-lead ECG
- Record concomitant medications and AEs
- Have subject complete the PRO assessments before any study-related procedures are performed
- Collect blood sample for CBC with differential and platelet count
- Collect blood sample for serum chemistries
- Collect urine sample for urinalysis (Section 9.7)
- Sparse PK: collect a blood sample for PK (Table 8.1)
- Collect blood sample for HAHA
- Perform a serum or urine pregnancy test for female subjects of childbearing potential
- Tumor measurement assessments unless it was performed within the previous 6 weeks or the previous assessment demonstrated disease progression
- Collect blood samples for additional biomarkers

If there is a significant clinical or laboratory abnormality in need of monitoring beyond the end-of-study treatment visit, subjects will be followed until resolution of the abnormality, until it is considered stable, or the subject begins another cancer treatment.

For subjects with positive HAHA at the end-of-study treatment visit, additional serum samples for HAHA and PK should be collected every 3 months until HAHA titers return to baseline or until the start of another cancer therapy. Samples will be collected up to 1 year from the last dose of study drug or collected up to the time that a subject starts another cancer therapy, whichever occurs first.

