### **6.2.11. Discontinuation From Study Treatment**

Subjects discontinued from study treatment without documented (by imaging) PD, withdrawal of consent, death or loss to follow-up should continue tumor evaluation at 6-week intervals up to the first 24 weeks after randomization, then every 12 weeks ( $\pm 7$  days) until disease progression, start of new anticancer therapy, death, withdrawal of consent, loss to follow-up, or study closure.

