## **8.4. Human Antihuman Antibodies**

The formation of antibodies to patritumab will be characterized by a screening test for HAHA and, if positive, a confirmatory test to determine antibody titers. If antibody titers indicate HAHA to patritumab are present, then the sample will be assayed to determine whether antibodies are neutralizing.

Blood samples will be collected within 3 days prior to Day 1 of Cycle 1 (baseline), Cycle 2 (preinfusion), Cycle 3 (preinfusion), and at End of Study Treatment visit. For subjects with positive HAHA at the End of Study Treatment visit, additional serum HAHA and PK samples should be collected every 3 months up to 1 year from the last dose of study

drug or if the subject starts another therapy for cancer, or withdraws consent from the study, whichever occurs first. Detection of HAHA formation in serum samples will be performed using validated assays.

For instructions on management of HAHA samples please refer to the laboratory manual.

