### **11.2. General Statistical Considerations**

This is a multicenter randomized Phase 2 study designed to evaluate the safety and efficacy of patritumab in combination with cetuximab and platinum-based therapy in recurrent/metastatic first-line SCCHN. The primary analyses for this study will occur when at least 53 PFS events have been observed in the HRG high stratum.

At the point of primary analysis for PFS, the treatment assignment for all randomized subjects will be unblinded to designated study personnel for the analysis after data are reconciled and cleaned and a snapshot of the clean database is created. To minimize potential bias, subjects and Investigators will not be informed about individual treatment assignment until study closure.

Final analyses will occur after study closure with mature OS data for the main study phase. At the time of study closure, subjects who are demonstrating clinical benefit (SD or better) from study treatment may be offered an opportunity to continue study treatment on the extension phase.

Assessments of change from baseline to post baseline or the ratio of post baseline to baseline will include only those subjects with both baseline and post baseline

measurements. The last nonmissing value of a variable taken before the first dose of study drug will be used as the baseline value, unless otherwise specified. In general, missing or dropout data will not be imputed for the purpose of data analysis. Descriptive summary statistics (n, mean, median, standard deviation, and range) will be calculated for continuous variables, and for categorical variables, the number and percentage in each category will be displayed by treatment group.

A detailed SAP describing the methodology will be prepared and finalized prior to primary analyses being performed and prior to database unblinding. Statistical methods described here may be modified based on advances in research. Any deviations and reasons for changes from the planned statistical analyses in the protocol will be fully described in the SAP and in the clinical study report.

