3.3.2. Blinding

This study is randomized, placebo-controlled, double blinded study. The treatment assignments will be blinded to the subjects, the investigators, site staff, and all persons involved in reviewing the clinical data, including CRO personnel in clinical and trial management and Sponsor personnel, with the exception of the Data Monitoring Committee, who will review the unblinded clinical data on an ongoing basis.

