3.3.2.1. Unblinding at Primary Analysis

At the point of primary analysis, as defined in Section 7 of this SAP, the treatment assignment for all subjects randomized will only be unblinded to CRO and sponsor statisticians and programmers directly involved in performing the analyses after data are reconciled and cleaned and a snapshot of the clean database is created. To minimize potential bias, subjects and investigators will not be informed about individual treatment assignment until study closure. Any datasets containing potentially unblinded information (i.e., patritumab PK and HAHA) will have their access restricted. The study statistician will maintain a list of the individuals who have access to individual treatment assignments and/or data that potentially unblinds the study. This list will include the date and level of unblinding and rationale for unblinding.

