8.2.1. Analysis of Primary Efficacy Variables

The primary efficacy endpoint is PFS as defined in Section 5.1.1 of this SAP. Progression will be determined based on the investigators' assessment.

The primary efficacy analysis will be the comparison of PFS between the patritumab arm and the control arm in HRG-high stratum of the FAS using the stratified log-rank test. For a description of the handling of censored data for efficacy endpoint PFS, see Section 5.1 above.

The testing hypotheses to compare PFS for the patritumab arm versus the control arm will be performed in two sequential steps (Freidlin 2012 et al). In step 1, the null hypothesis that PFS is the same for both arms in the HRG high stratum of FAS is tested at the one-sided 0.10 significance level. If this test in step 1 does not reject the null hypothesis, then in step 2A, the null hypothesis that PFS is the same for both arms in the FAS (HRG high stratum + low stratum) will be tested at the one-sided 0.05 significance level. If the test in step 1 is rejected, then in step 2B, the two-sided 80% confidence interval (CI) for hazard ratio (HR) of PFS in the HRG low stratum of the FAS will be estimated.

The comparison of PFS between the patritumab arm and the control arm will be performed using a log-rank test stratified by the stratification factors.

Hypothesis testing for superiority with regard to PFS will be performed with a 1-sided hypotheses setting.

Suppose that $S_A(t)$ and $S_P(t)$ are the cumulative survival functions for PFS in patritumab and control treatment groups, respectively. The null hypothesis H_0 with PFS:

$$H_0: S_A(t) = S_P(t) \text{ for all } t \geq 0 \text{ (identical survival functions for both groups)}$$

will be tested against the 1-sided alternative hypothesis H_A :

$$H_A: S_A(t) \geq S_P(t) \text{ for all } t \geq 0 \text{ and } S_A(t) > S_P(t) \text{ for at least some } t > 0$$

(improvement in PFS in the patritumab group over the control group)

The stratified log-rank test will be conducted using SAS PROC LIFETEST where the STRATA statement will include the treatment group and the stratification factors [HPV (positive vs other) and HRG (high vs. low, only for the FAS) at randomization]. The 1-sided p-value will therefore be obtained and H_0 will be rejected if p-value \leq the pre-specified 1-sided alpha.

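### Protocol 9.11.2 sends HAHA results to the sites with no timing or masking, which conflicts with the site blind under investigator-assessed PFS; through HAHA alone the exposure is small

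*Protocol*

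**What the plan says.** **Release to sites.** Protocol 9.11.2 schedules HAHA samples before infusion at Cycles 1, 2 and 3 and at the End-of-Study Treatment visit. It adds a simultaneous PK sample "for interpretation of HAHA results, which will be provided to the study sites". It does not say when results are sent, in what form, or to whom at the site. SAP 5.2.6 repeats the schedule but leaves out that sentence, while SAP Section 9 records no change from the protocol.

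**Blinding.** SAP 3.3.2: "The treatment assignments will be blinded to the subjects, the investigators, site staff". The Data Monitoring Committee is the stated exception. Protocol 11.2: "subjects and Investigators will not be informed about individual treatment assignment until study closure". SAP 3.3.2.1: "Any datasets containing potentially unblinded information (i.e., patritumab PK and HAHA) will have their access restricted".

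**Who reads PFS.** SAP 8.2.1: "Progression will be determined based on the investigators' assessment". Neither document describes a blinded independent review of scans. The PFS sensitivity analyses (SAP 8.2.1 and 8.2.4.1) deal with clinical progression and a changed HRG cutoff, not with assessors who may know the arm.

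**What the site does with a positive result.** Protocol 6.2.9: "For subjects with positive HAHA at the end-of-study treatment visit, additional serum samples for HAHA and PK should be collected every 3 months". Protocol 4.1.5, 8.4 and 9.11.2 contain similar conditional sampling; 4.1.5 and 9.11.2 tie it to neutralizing antibody.

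**Scans after treatment stops.** Protocol 6.2.11: "Subjects discontinued from study treatment without documented (by imaging) PD" continue tumor evaluation, apart from the exceptions listed there.

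**The concern.** Subjects on placebo receive no patritumab, so a new anti-patritumab antibody after dosing points to the patritumab arm. The SAP recognizes this by restricting the data. The protocol sends the same kind of data to the people who must stay blinded and who decide when progression occurred.

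That decision involves judgement. Protocol 7.1 lets equivocal findings be carried to the next scan and back-dated if confirmed, and Appendix 17.3.2.5.1 asks for a judgement on unequivocal worsening of non-target disease. With no central review, the blind at the site is the main protection against assessment bias.

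Protocol 5.1.9 surrounds emergency code breaks with controls: a call to the CRO medical monitor within 24 hours, and the assignment kept out of the subject's source files. A HAHA report sent to the site has no comparable control.

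**Working it through.** **1. Design figures, for context.** Inputs from Protocol 11.10: HR 4.2/7.5 = 0.56, one-sided alpha 0.10, 80% power, 1:1 allocation. Schoenfeld's formula gives events = 4(z₀.₉₀ + z₀.₈₀)² / (ln 0.56)² = 4(1.2816 + 0.8416)² / 0.3362 = 53.6, against 53 planned. Power at 53 events is 79.6%. At 75 events and one-sided 0.05 it is 80.7%, against 81% stated. The plan's figures reproduce, and nothing below alters them.

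**2. Can a result arrive before the PFS event?** The Cycle 1 sample precedes dosing and cannot reflect the arm. The Cycle 2 and Cycle 3 samples follow a dose and may precede progression. The end-of-treatment sample comes after the event in a subject who stopped for radiographic progression. It can precede the event in a subject who stopped without imaging progression and is still being scanned under 6.2.11. Early arrival is therefore possible by two routes, but with no release date in 9.11.2 it is not established. Separately, the conditional sampling means that, as written, the site must learn of a positive end-of-treatment result, possibly before closure.

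**3. How many subjects?** Incidence p is taken as 1%, the upper figure in Protocol 1.1.1.5. With 1:1 allocation the patritumab arm has 70/2 = 35 HRG-high subjects and 105/2, about 53, overall. Expected positives = np; chance of at least one = 1 − (1 − p)ⁿ.

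| Incidence | HRG-high, n = 35 | Whole arm, n about 53 |
|---|---|---|
| 0.5% (assumed) | 0.18 expected; 16% chance of any | 0.27; 23% |
| 1% (Protocol upper figure) | 0.35; 1 − 0.99³⁵ = 30% | 0.53; 1 − 0.99⁵³ = 41% |
| 5% (assumed) | 1.75; 83% | 2.65; 93% |
| 10% (assumed) | 3.5; 98% | 5.3; above 99% |

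At 1%, the chance of two or more is 5% in HRG-high and 10% in the whole arm. These counts include positives found only after the PFS event, so the number that could affect assessment is smaller.

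**4. What does a result reveal?** With no false positives, P(patritumab | negative) = (1 − p)/[(1 − p) + 1]. This is 0.99/1.99 = 49.7% at 1% and 0.90/1.90 = 47.4% at 10%, so a negative result says almost nothing. A positive identifies the arm if there are no false positives. If the false-positive rate f were 1% in both arms (an assumption), P(patritumab | positive) = [p + (1 − p)f]/[p + (1 − p)f + f] = 0.0199/0.0299 = 67%.

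**5. Patritumab concentrations.** A measurable post-dose concentration would reveal the arm for essentially any dosed subject with such a sample. On its natural reading, however, the sentence in 9.11.2 sends HAHA results to the sites; the PK sample is there to help interpret them.

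**The case against.** The strongest reply is that fewer than one informative subject is expected among 70 HRG-high subjects, so a bias in PFS that anyone could detect is unlikely. That stands for HAHA alone. It rests on earlier experience, though: HAHA incidence in this combination is itself a secondary objective (Protocol 2.1.2).

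Second, SAP 3.3.2.1 speaks of datasets, calls them only potentially unblinding, and sits under unblinding at the primary analysis. It does not expressly govern a report on one subject to one site. This also stands. The firmer conflict is with SAP 3.3.2 and Protocol 11.2, which blind the site without that qualification.

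Third, Protocol 8.4 refers HAHA sample management to a laboratory manual, which might control reporting. That document is not available here, and 9.11.2 points to no such control.

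A reader might infer more: that every treated subject at a site is revealed through PK, that PFS assessors as a group are unblinded, or that any positive proves the arm. The documents do not support these readings. No passage clearly sends concentrations to sites, and only positive results are informative. A baseline sample is taken, and 9.11.2 follows positives until they return to that baseline, so the plan allows for some reactivity before dosing.

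**Conclusion.** The conflict is real and should be corrected. The protocol promises HAHA results to sites that must remain blinded, gives no timing or masking, and has the same sites assess the primary endpoint.

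The size through HAHA alone is small: 0.35 expected positives in the HRG-high patritumab arm (30% chance of any) and 0.53 in the whole arm (41%), some known only after the PFS event. These figures assume 1:1 allocation and 1% incidence. A higher incidence would raise them, as the table shows.

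The exposure would be large only if a laboratory took the loosely attached relative clause in 9.11.2 to cover the paired PK results. That is a risk created by the wording, not something the plan prescribes. Actual release before progression is possible but not shown. No change to sample size or testing follows.

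**What to change.** In Protocol 9.11.2, replace the clause on provision to sites with a statement that HAHA and patritumab PK results are withheld from sites and from blinded sponsor and CRO staff until study closure. Align SAP 3.3.2.1 and 5.2.6 with it.

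Deleting the clause is not enough, because the conditional sampling in Protocol 4.1.5, 6.2.9, 8.4 and 9.11.2 needs someone to tell the site. Write in a named exception. For example, the laboratory or another party already unblinded notifies the site of a positive end-of-treatment result only once the PFS event is documented or PFS follow-up has ended. Any earlier release is logged. An alternative is to sample both arms alike, so that a request reveals nothing, at the price of extra blood draws.

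The emergency route in Protocol 5.1.9 does not suit routine antibody reporting: it is reserved for rare emergencies and ties a code break to stopping study treatment.

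The cost is a small change to the laboratory reporting procedure. Under the delayed notice, HAHA follow-up samples may be late or missed in the rare positive subject without documented progression.

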## 10. OTHER ASSESSMENTS

### 10.1. Eastern Cooperative Oncology Group Performance Status

The ECOG performance status will be determined at Screening, and then at each scheduled visit throughout the study. See Table 10.1 below.

**Table 10.1: Eastern Cooperative Oncology Group Performance Status Scale Grade Description**

0	Normal activity. Fully active, able to carry on all pre-disease performance without restriction.
1	Symptoms, but ambulatory. Restricted in physically strenuous activity, but ambulatory and able to carry out work of a light or sedentary nature (eg, light housework, office work).
2	In bed <50% of the time. Ambulatory and capable of all self-care, but unable to carry out any work activities. Up and about more than 50% of waking hours.
3	In bed >50% of the time. Capable of only limited self-care, confined to bed or chair more than 50% of waking hours.
4	100% bedridden. Completely disabled. Cannot carry on any self-care. Totally confined to bed or chair.
5	Dead.

Source: Oken MM, Creech RH, Tormey DC, Horton J, Davis TE, McFadden ET, et al. Toxicity and Response Criteria of the Eastern Cooperative Oncology Group. *Am J Clin Oncol*. 1982;5:649-55.

### 10.2. Patient-Reported Outcomes

Patient-reported outcomes will be used to evaluate study treatment in subjects treated with patritumab + cetuximab + platinum-based therapy compared to placebo + cetuximab + platinum-based therapy (see [Appendix 17.2](#)).

#### 10.2.1. Functional Assessment of Cancer Therapy—Head and Neck (FACT-H&N) Instrument

The FACT-H&N is a multidimensional, self-report quality of life instrument specifically designed for use with head and neck cancer patients. It consists of 28 core items, the FACT-G, which assess patient function in four domains: Physical, Social/Family, Emotional, Functional well-being, and relationship with doctor which is further supplemented by 12 head and neck-specific items to assess head and neck related symptoms, and form the FACT-Head and Neck Subscale (HNS). Each item is rated on a 0 to 4 Likert type scale, and then combined to produce subscale scores for each domain, as well as a global QoL score. Higher scores represent better quality of life.

Ten items of the FACT-H&N also form a symptom related index, FHNSI-10, which can be analyzed separately.

